## 11.3 Amendments to the protocol

To alter the protocol, amendment approvals must be received from all parties that approved the original protocol (IRB and if applicable, the local regulatory authorities) before implementation. However, in cases where an amendment is required for subject safety, an amendment may be implemented prior to IRB approval. Notwithstanding the need for approval of formal protocol amendments, the investigator or designee is expected to take any immediate action required for the safety of any subject included in this study, even if this action represents a deviation from the protocol.

CoLucid Pharmaceuticals may make administrative changes (i.e., changes that do not significantly affect subject safety, the study's scope or scientific quality) without a formal protocol amendment.

# 11.4 Discontinuation of the study

CoLucid Pharmaceuticals reserves the right to discontinue this study under the conditions specified in the clinical trial agreement.

# 11.5 Study drug supply, storage and tracking

Study drug must be received by a designated person at the study site, handled and stored safely and properly, and kept in a secured location to which only the investigator and designated assistants have access. Upon receipt, study drug should be stored according to the instructions specified on the drug labels. Drug labels will be in the local language and will comply with the legal requirements of the country. Clinical supplies are to be dispensed only in accordance with the protocol.

All empty packaging, partially used containers, and unused supplies may be destroyed at the site, retrieved by the study monitor, or shipped to a designated facility approved by CoLucid Pharmaceuticals according to governmental regulations at the conclusion of this study (or as appropriate during the course of the study), per the instructions of the Sponsor.

The Investigator or designee will keep an accurate accounting of all study drug dispensed, destroyed or returned. Monitoring of drug accountability will be performed by the monitor during site visits and at the completion of the trial.

## 11.6 Confidentiality

All study findings and documents will be regarded as confidential. The Investigator and other study personnel must not disclose such information without prior written approval from CoLucid Pharmaceuticals.

Subject confidentiality will be strictly maintained to the extent possible under the law. Subject names must not be disclosed. Subjects will be identified on the CRFs and other documents submitted to CoLucid Pharmaceuticals, or its designated representative, by their initials and/or assigned subject number. Documents that identify the subject (e.g., the signed informed consent form) will not be submitted to CoLucid Pharmaceuticals or its designated representative and must be maintained in confidence by the Investigator and designee.

## 11.7 Publication policy

Publication by the study site or Investigator/Institution will not be allowed without the explicit written permission of the Sponsor. The Sponsor will determine authorship of the principal study manuscript(s) in conjunction with the Investigator, in accordance with current guidelines and requirements of medical journals.

### 12.2 Records Retention

After the study, the Investigator or designee will keep all information relevant to the study for 15 years.

# 15. Appendix 2. Visual Analogue Scales (VAS)

[figure not shown]
# **Bipolar Drug liking**

[figure not shown]
### **Bipolar High**

# **Unipolar Sedation**

## **Unipolar Overall Drug Liking**

[figure not shown]

[figure not shown]

# **VAS Training Scales**

### Bipolar: My dinner last night was...

The worse I have ever had

Neither good nor bad

The best I have ever had

### Unipolar: The weather yesterday was great

# LIST OF ABBREVIATIONS

Abbreviation	Definition
AE	Adverse Event
ALT	Alanine Aminotransferase
ANOVA	Analysis of Variance
AST	Aspartate Aminotransferase
ALT	Alanine Aminotransferase
AP	Alkaline Phosphatase
ATC	Anatomic-Therapeutic-Chemical
AUC	Area Under the Plasma Concentration Versus Time Curve
AUC (0-last)	Area under the plasma concentration versus time curve from time 0 to last post-dose
$\mathrm{AUC}_{(0^{-\infty})}$	Area under the plasma concentration versus time curve from time 0 to infinity
BMI	Body Mass Index
BQL	Below Quantification Limit
CBC	Complete Blood Count
C max	Maximum Measured Plasma Concentration
СРК	Creatine Phosphokinase
CRU	Clinical Research Unit
C-SSRS	Columbia Suicide Severity Rating Scale
CV	Coefficient of Variation
CYP3A4	Cytochrome P450 3A4, an enzyme
DDI	Drug-Drug Interaction
DEQ-5	Drug Effects Questionnaire
ECG	Electrocardiogram
eGFR	Glomerular Filtration Rate
EOS	End of Study
eCRF	Electronic Case Report Form

Abbreviation	Definition
EW	Early Withdrawal
HBsAg	Hepatitis B Surface Antigen
HCV	Hepatitis C Virus
HDL	High-Density Lipoprotein
HIV	Human Immunodeficiency Virus
IMP	Investigational Medicinal Product
LDL	Low-Density Lipoprotein
LOQ	Limit of Quantification
LS	Least-Squares
MCHC	Mean Corpuscular Hemoglobin Concentration
MCV	Mean Corpuscular Volume
MedDRA	Medical Dictionary for Regulatory Activities
PD	Pharmacodynamic
PK	Pharmacokinetic
PKE	Pharmacokinetic Evaluation
RBC	Red Blood Cell
SAP	Statistical Analysis Plan
TEAE	Treatment Emergent Adverse Event
t1/2	Apparent terminal elimination half-life
THC	Tetrahydrocannabinol
T max	Time to Reach Maximum Measured Plasma Concentration
VAS	Visual Analog Scale
Vd/F	Apparent Volume of Distribution
WBC	White Blood Cell
WHO	World Health Organization
$\lambda_{\rm z}$	Apparent First-Order Terminal Elimination Rate Constant

#### 1. INTRODUCTION

Lasmiditan is being developed as a novel acute therapy for migraine. Migraine is a common neurological disorder and was ranked by the World Health Organization (WHO) in its 2010 Global Burden of Disease survey as one of 7 most debilitating conditions, and as the third most common disease in the world among both males and females. Five Phase 1 studies have been completed in Europe using intravenous (IV), sublingual, and oral formulations of Lasmiditan. This study is designed to assess the effect of single doses of Sumatriptan (Imitrex) 100 mg on the pharmacodynamics of single doses of Lasmiditan 200 mg as measured by serial vital signs, ECGs, and adverse events. Safety and tolerability will also be reported.

The purpose of this statistical analysis plan (SAP) is to provide all details and specifications for the analysis of the study COL MIG-118, "A Randomized, Double-Blind, Three Period, Cross-Over Study to Evaluate the Effect of Single Oral Doses of Lasmiditan when Coadministered with Single Oral Doses of Sumatriptan (Imitrex) in Healthy Male and Female Subjects' "as set forth in the clinical study protocol version 1.0 dated 17 February 2017.

### 2. STUDY DETAILS

# 2.1 Study Objectives

The study objectives are:

**Primary Objective-** To compare and contrast the pharmacodynamics of Lasmiditan 200 mg and Sumatriptan (Imitrex) 100 mg administered together to the pharmacodynamics of single doses of either drug administered alone.

## **Secondary Objective-**

- To compare and contrast the pharmacokinetics of Lasmiditan 200 mg and Sumatriptan (Imitrex) 100 mg administered together to the pharmacokinetics of single doses of either drug administered alone.
- To evaluate the safety and tolerability of Lasmiditan 200 mg and Sumatriptan (Imitrex) 100 mg administered together to the safety and tolerability of single doses of either drug administered alone.
- To compare and contrast the subjective drug effects of Lasmiditan 200 mg and Sumatriptan (Imitrex) 100 mg administered together to the subjective drug effects of single doses of either drug administered alone.

# 2.2 Study Design

This is a Phase 1, single-center, randomized, double-blind, three-period, cross-over study to investigate the effect of single doses of Sumatriptan (Imitrex) 100 mg on the

pharmacodynamics of single doses of Lasmiditan 200 mg. A total of 42 subjects will be enrolled to ensure at least 36 subjects complete the study with approximately 60% females.

The three dosing periods are as follows-

- A: Lasmiditan 200 mg co-administered with Lasmiditan 200 mg placebo
- B: Sumatriptan (Imitrex) 100 mg co-administered with Lasmiditan 200 mg placebo
- C: Lasmiditan 200 mg co-administered with Sumatriptan (Imitrex) 100 mg

Subjects are randomized using the William square design into one of the six treatment sequences ABC, ACB, BAC, BCA, CAB, CBA.

The study will last approximately 6 weeks including up to 3 weeks for screening and 22 days on study. Screening will be conducted within approximately 21 days of the first dose of study medication. Each dosing period will last 3 days (Day -1, Day 1, and Day 2). A wash-out period of 6 days will take place between each dose. The End of Study Visit (EoS) will take place 5 (+/- 2) days after the third dosing period is completed.

#### 3. DATA ANALYSIS CONSIDERATIONS

# 3.1 Determination of Sample Size

The sample size calculation for this study is based on the proportion of adverse events in the two treatment groups namely the combination therapy (Lasmiditan + Sumatriptan) vs a single drug (Lasmiditan). The calculation is performed using a test for two proportions in a repeated measures design. To ensure that at least 36 subjects complete, 42 subjects (approximately 60% female) will be enrolled.

The sample size of 36 subjects will provide at least 80% power to show equivalence of the PK of Lasmiditan in the absence and presence of Sumatriptan (Imitrex), assuming a 25% within subject coefficient of variance.

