Treatment-emergent adverse events (TEAEs) were reported by 22% of the subjects receiving placebo and by 65, 73, 86 and 84% of subjects receiving 50, 100, 200 and 400 mg lasmiditan, respectively. The most common adverse events seen in the lasmiditan groups were related to the nervous system. These included dizziness, fatigue, vertigo, somnolence and paresthesia. Chest symptoms characteristic of triptan use were rare and occurred with a similar frequency in the placebo and active groups.

The first Phase 3 double-blind, placebo-controlled, parallel-group study of lasmiditan evaluated the proportion of subjects who were headache pain-free at 2 hours post-dose, safety, and other measures of migraine pain relief (clinical study COL MIG-301, SAMURAI). The study compared 100 mg and 200 mg doses of lasmiditan with placebo in 2232 adult subjects who treated one acute migraine attack. In this study both doses of lasmiditan were statistically significant over placebo (p<.001) on the primary endpoint of headache pain free at 2 hours post dose and on the key secondary endpoint of most bothersome symptom free at 2 hours post dose. 

During the clinical development of lasmiditan, there have been no deaths and no subjects have been withdrawn due to adverse events. One serious adverse event (SAE) of moderate dizziness leading to overnight hospitalization was reported in the oral dose-ranging study. This occurred in a female patient given lasmiditan 200 mg, and resolved without sequelae. Across the clinical trials in the lasmiditan development program, somnolence, dizziness, and fatigue have been the mostly frequently reported adverse events. The sponsor has thus advised subjects in ongoing trials to not drive or operate machinery for 12 hours after dosing and plans to complete a skilled performance study.

More information on the preclinical and clinical experience with lasmiditan are given in the Clinical Investigators' Brochure (IB). [10]

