## 8.1 Sample Size

To ensure that at least 36 subjects complete, at least 42 subjects (approximately 60% female) will be enrolled.

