# 8.5 Pharmacokinetic Analyses

All evaluable subjects will be included in the PK analysis. The evaluable PK population will include all subjects who completed at least one treatment period without any protocol violations that would likely affect the PK results, who have evaluable plasma concentration data for lasmiditan and/or sumatriptan (Imitrex), and for whom at least a subset of the designated PK parameters can be determined.

Data will be summarized using descriptive statistics (sample size, mean, median, standard deviation, minimum, and maximum) for continuous variables and using frequency and percentage for discrete variables for each treatment unless additional analysis is deemed appropriate based upon a review of the PK results.

Standard PK parameters ( $C_{max}$ ,  $t_{max}$ ,  $t_{1/2}$  and AUC [AUC(0-last) and AUC(0-∞)] of lasmiditan 200 mg will be used to describe the characteristics of the drug when co-administered with sumatriptan (Imitrex) or when taken alone.

The primary statistical analysis will use the paired t-test applied to log-transformed PK parameter (lasmiditan Cmax or AUC30 separately) in the lasmiditan/sumatriptan (Imitrex) treatment period paired with the same subject's parameter value in the lasmiditan treatment period. From this model the means for each treatment and mean differences to the reference lasmiditan treatment will be estimated with the corresponding 90% confidence intervals. These estimates will then be exponentiated to produce the estimates of geometric mean ratios with their 90% confidence intervals. It will be concluded that sumatriptan (Imitrex) has no effect on lasmiditan PK, if 90% confidence intervals for ratios of PK parameters derived in lasmiditan/sumatriptan (Imitrex) treatment period to those derived in lasmiditan treatment period are within the 80-125% interval.

The sample size of 36 subjects will provide at least 80% power to show equivalence of the PK of lasmiditan in the absence and presence of sumatriptan (Imitrex), assuming a 25% within subject coefficient of variation.

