#### **Adverse Events**

Adverse Events will be coded using the Medical Dictionary of Regulatory Activities (MedDRA version 20.0) AE coding system for purpose of summarization.

An AE will be defined as treatment-emergent (TEAE) if its time of onset or worsening is on or after the time of the study drug administration.

An AE will be defined as treatment related if its relationship to the study drug is recorded as Possibly Related or Related on the eCRF.

An overall summary of number of events and number and percentage of subjects with at least one AE, TEAE, serious TEAE, treatment-related TEAE, serious treatment-related TEAE and TEAE leading to discontinuation will be presented.

A summary of the frequency (number and percentage of subjects with events) of TEAEs will be presented by system organ class, preferred term, and treatment group. Adverse events will also be analyzed by their severity (mild, moderate, severe, life threatening or fatal) and relationship to study drug (related or not related).

A subject experiencing the same AE multiple times will be counted only once for that preferred term. Similarly, if a subject experiences multiple AEs (preferred terms) within the same system organ class then that subject will be counted only once for that system organ class. When summarizing by severity and relationship, only event with highest severity or relationship will be counted. All AEs will be presented in alphabetical order of system organ classes and preferred terms.

All information pertaining to adverse events noted during the study will be listed by subject, detailing verbatim term given by the investigator, preferred term, system organ class, start date, stop date, severity, outcome, action taken and drug relatedness. Separate listings will be created for Serious TEAEs and TEAEs leading to study drug discontinuation if deemed necessary.

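### SAP 3.1 attributes the sample size to an adverse-event test whose inputs are not stated, and SAP 6.4.7 leaves out the between-treatment TEAE comparison that protocol 8.4.1 plans

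*SAP*

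**What the plan says.** **Sample size in the SAP.** Section 3.1 opens: "The sample size calculation for this study is based on the proportion of adverse events in the two treatment groups", meaning lasmiditan plus sumatriptan against lasmiditan alone. It continues: "The calculation is performed using a test for two proportions in a repeated measures design". Then: "To ensure that at least 36 subjects complete, 42 subjects (approximately 60% female) will be enrolled". A second paragraph adds: "The sample size of 36 subjects will provide at least 80% power to show equivalence of the PK of Lasmiditan", at a 25% within-subject coefficient of variation.

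**Sample size in the protocol.** Section 8.1 says only: "To ensure that at least 36 subjects complete, at least 42 subjects (approximately 60% female) will be enrolled". It gives no statistical reason for 36. Section 8.5, like the synopsis, says: "The sample size of 36 subjects will provide at least 80% power to show equivalence of the PK of lasmiditan", with the same 25%. Neither place mentions an adverse-event calculation.

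**Adverse-event analysis.** Protocol 8.4.1 plans a general linear random model to compare TEAE frequency across the three treatments. In SAP 6.4.7 the adverse-event plan is descriptive: "A summary of the frequency (number and percentage of subjects with events) of TEAEs will be presented", by system organ class, preferred term and treatment, with further tables by severity and relationship. The SAP gives no model, test, between-treatment difference or confidence interval for adverse events.

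**Role of adverse events.** The protocol synopsis includes them in the primary endpoint, and SAP 4.1 names them and vital signs as the PD endpoints. The primary objective in both documents is to compare the combination with each drug alone.

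**Background rate.** Protocol 1.2 reports TEAEs in the oral Phase 2 migraine trial as "65, 73, 86 and 84% of subjects receiving 50, 100, 200 and 400 mg lasmiditan", against 22% on placebo.

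**The concern.** A sample-size statement should let a reader recompute the number and should refer to an analysis that will be run. SAP 3.1 does neither for adverse events. No input is given, and the SAP contains no analysis to which the calculation could belong.

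The consequence is for interpretation. Someone reading SAP 3.1 would take the trial to be sized to compare adverse events between combination and lasmiditan. If the percentages then look similar, that similarity could be read as evidence of no interaction on a primary PD endpoint, with no stated power, no estimate of the difference and no interval behind it.

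**Working it through.** **1. Reproduce the power figure that has inputs (PK).** Inputs from protocol 8.5: n = 36, within-subject CV 25%, 90% CI within 80–125%, paired analysis on the log scale. The true ratio is not stated, so a range is shown.

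- Within-subject SD on the log scale: √ln(1 + 0.25²) = √ln(1.0625) = 0.246.
- Standard error of the mean paired difference: √(2 × 0.246² / 36) = 0.058.
- Power of two one-sided paired t-tests at 5%, 35 df:

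| Assumed true ratio | Power, n = 36 |
|---|---|
| 1.00 | 96.6% |
| 0.95 | about 89% |
| 0.92 | 76.3% |
| 0.90 | 63.5% |

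The claim of at least 80% holds for ratios of 0.95 to 1.00. The smallest n for 80% is 23 at a ratio of 1.00 and 28 at 0.95. The PK inputs support 36 but do not single it out.

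**2. Try to reproduce 36 from the adverse-event basis.** This needs two rates, a correlation (or discordance), alpha, sidedness and power. None is stated, so it cannot be done. The step from 36 to 42 is only attrition: (42 − 36)/42 = 14.3%.

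**3. Illustration at the one 200 mg TEAE rate in the documents.** Assumption: 86% on lasmiditan alone, borrowed from migraine patients. Take the largest possible rise, to 100% on the combination. Every discordant pair then points the same way, and the number of such pairs is Bin(36, 0.14), with mean 36 × 0.14 = 5.04.

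- Exact McNemar, two-sided 5%: five pairs in one direction give 2 × 0.5⁵ = 0.0625 and six give 2 × 0.5⁶ = 0.031, so six are needed. Power = P(Bin(36, 0.14) ≥ 6) = 39%.
- Mid-p: five are enough (p = 0.031). Power = P(≥ 5) = 58%.
- Uncorrected asymptotic: four are enough (z = √4 = 2, p = 0.046). Power = P(≥ 4) = 76%.

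| Test, two-sided 5%, 86% to 100% | 36 pairs | 42 pairs | Pairs for 80% |
|---|---|---|---|
| Exact McNemar | 39% | 55% | 55 |
| Mid-p | 58% | 72% | 47 |
| Uncorrected asymptotic | 76% | 86% | 39 |

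**4. How far this depends on the assumptions (36 pairs).**

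- One-sided 5%, 86% to 100%: 58% exact, 76% mid-p, 90% uncorrected asymptotic.
- 80% to 100%, two-sided: 75% exact, 87% mid-p, 95% uncorrected asymptotic.
- 50% to 75%, two-sided exact: 82% at within-subject correlation 0.5, 50% at correlation 0.

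**5. Precision that 36 completers give.** The 95% half-width for a paired risk difference near zero is 1.96 × √(d/36), where d is the assumed proportion of discordant pairs.

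- d = 0.20: 1.96 × 0.0745 = 0.146, about 15 points.
- d = 0.40: 1.96 × 0.1054 = 0.207, about 21 points.

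**The case against.** The strongest reply is that nothing here is shown to be miscalculated. An adverse-event basis accompanied by a PK power statement is not a contradiction, because the PK sentence says what 36 achieves and need not be where 36 came from. The 86% is from patients treating a migraine attack in a parallel-group trial, whereas this trial enrols healthy subjects, for whom the documents give no TEAE rate at 200 mg. The outcome behind the SAP calculation might be something other than any TEAE, and the SAP fixes neither the test nor its sidedness. All of that stands.

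It rules out three stronger readings that a reader might draw:

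- *That no adverse-event comparison is planned at all.* Protocol 8.4.1 plans one. The gap is in the SAP.
- *That the protocol derives 36 from PK.* Section 8.1 gives no basis, and 8.5 only reports the PK power of 36.
- *That 36 subjects cannot support an adverse-event comparison.* Step 4 shows inputs under which they can.

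The sponsor could add that the protocol synopsis also treats adverse events descriptively, so the SAP follows that summary. But protocol section 8 says the SAP will supply detailed methods for the analyses outlined there, and 8.4.1 is one of them. The SAP does not say that the model has been replaced.

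**Conclusion.** The point holds in two parts. First, the adverse-event basis in SAP 3.1 cannot be reproduced, because every input is missing. Whether the calculation was done, and with what inputs, cannot be known from the documents. Second, followed as written, the SAP makes no between-treatment adverse-event comparison on a primary PD endpoint, although the protocol plans one. Both parts rest on the text alone.

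The power figures are an illustration. They assume an 86% rate in healthy subjects, any TEAE as the outcome, a rise rather than a fall, and a two-sided 5% test. On those assumptions power at 36 pairs stays below 80% for all three tests (39% to 76%) even at the largest possible rise. With other rates, correlations or a one-sided test it can exceed 80%. This is a matter to correct before analysis; it does not call the enrolment figure into question.

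**What to change.** **SAP 3.1.** Do one of two things:

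- State the inputs of the adverse-event calculation (outcome, both rates, correlation, alpha, sidedness and test) and the power they give at 36.
- Or withdraw the adverse-event basis and say that 36 is supported by the PK equivalence power, with the assumed true ratio. Then add the precision for the paired TEAE risk difference: about 15 points at 20% discordance and 21 points at 40%. This keeps the primary PD objective from being left without any statement of what 36 can show.

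**SAP 6.4.7.** Restore the TEAE comparison of protocol 8.4.1 with its model specified, or explicitly replace it with the paired TEAE risk difference, combination minus each single drug, with its confidence interval. If it is replaced, record the change from the protocol.

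**Cost.** SAP wording and a little more analysis. The stated adverse-event justification may look less favourable. Enrolment and data collection do not change.
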